5.9 Biomarker Assessment

Biomarker studies will be carried out at UW Hospital by performing immunohistochemistry analyses on the original diagnostic biopsy material whenever this is available. In most cases, this will be needle biopsy material. The emphasis will be on a proliferation markers, Ki-67 and apoptotic pathway markers (e.g., p53, bcl-2, bax and mdm-2). The apoptotic markers are all involved in molecular radiation response pathways and have shown promise in predicting prostate cancer patient outcome after radiotherapy, while the proliferation marker, Ki-67, may have particular relevance for hypofractionation since the slow proliferation typical of many prostate cancers is thought to be causally related to their high capacity for interfraction repair and their suitability for a hypofractionated radiotherapy approach. All of these markers will be determined by quantitative immunohistochemistry, using the ACIS Chromavision system, as has been used, for example, in immunohistochemistry studies carried out in RTOG 86-10 (37).

Clinical outcomes (biochemical control) determined from the trial described here will not be ready for correlative analysis comparisons with these biomarker analysis for approximately 7 years. This analysis is for research purposes only and is not expected to have an impact on the patients enrolled on this study.

6.0 MEASUREMENT OF EFFECT

6.1 General

The primary objectives of this study are to potentially establish the maximum tolerated hypofractionation intensity (or to determine whether the most hypofractionated schedule tested in this study is tolerated) for prostate cancer patients and to determine clinical response. Analyses for

clinical tumor control and PSA disease free survival will be performed when median 5-year follow-up is obtained. Data will be collected for efficacy evaluation as stated in section 6.2 and 6.3.

6.2 Disease-free Status

Patients will be considered to be without biochemical recurrence if either the PSA is still declining or the PSA nadir has been reached and is below 1.0 ng/mL, there is no palpable or radiologic evidence of disease, PSA is not rising (defined as 3 successive increases in measured PSA levels each at least two months apart) and there is no evidence of metastasis. Patients not meeting these criteria will be judged to have a recurrence.

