3.0 SELECTION OF PATIENTS

- Histologically proven adenocarcinoma of the prostate.
- Stage ≤ T2b disease, as defined by 1997 AJCC classification
- Predicted risk of lymph node involvement (by standard nomograms) of 15% or less (24), OR histologically negative pelvic nodes
- Gleason score ≤ 7
- No evidence of distant metastasis
- Age 18+
- Informed consent signed in accordance with institutional protocol
- Pretreatment evaluations must be completed as specified in Section 7.0.
- ECOG performance status 0-1
- No previous or concurrent cancers, other than localized basal cell or squamous cell skin carcinoma, unless continually disease free for at least 5 years
- No prior pelvic irradiation, prostate brachytherapy, or bilateral orchiectomy
- Gonadotropin-releasing hormone agonist (GnRH-a) use permitted (maximum of 6 months duration). Anti-androgen therapy permitted concurrently with GnRH-a.
- No previous or concurrent cytotoxic chemotherapy
- No radical surgery or cryosurgery for prostate cancer
- The absence of any co-morbid medical condition which would constitute a contraindication for radical radiotherapy
- The absence of serious concurrent illness of psychological, familial, sociological, geographical or other concomitant conditions which do not permit adequate follow-up and compliance with the study protocol.
- No current use of anticoagulation therapy, other than aspirin.

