6.3 Progressive Disease

Any patient with rising PSA on 3 successive serum measurements will be considered to have recurrent or progressive disease. The date of failure will be taken as midway between the nadir PSA date and the date of the first of the three rising PSAs.

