7.0 STUDY PARAMETERS

7.1 All pre-study laboratory tests must be done within 6 weeks of registration.

7.2 Patients will be evaluated weekly during radiotherapy by one of the clinical study investigators to assess acute toxicities and functional status

7.3. The follow-up schedule and evaluations are outlined below:

	Pre-study	Weekly during RT	4 weeks post-RT	3 months post-RT	Subsequent follow-up ^a
H & P	X		X	X	X
Weight	X	X	X	X	X
Performance status	X	X	X	X	X
PSA	X		X	X	X
CBC/platelets	X				
Toxicity notation	X	X	X	X	X
QOL assessment	X				X ^b
IPSS score	X		X	X	X

^a Subsequent follow-up will be every 3 months x 1 year post-treatment, every 4 months during years 2 - 3, every 6 months years 4 – 5 and then annually. Follow-up frequency can be increased if thought medically necessary by the treating physician

^b QOL assessment will be completed pre-treatment and at 12, and 24 and 36 months post-treatment.

* For patients for whom travel to the treating institution creates a hardship, scheduled follow-ups, with the exception of the 4 week and all annual follow-ups, can be conducted via telephone interview with PSA and any other indicated testing being carried out at a facility near to the patient.

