8.2 Disease-free Survival

A primary endpoint is Disease-Free Survival (DFS), as defined in Section 6.2. The 95% confidence interval for DFS observed on 150 fully followed patients will have half-width of 8% or less; that is, it will be the observed DFS rate plus or minus 8%. This figure is conservative in that the width will be less for DFS rates far from 50%. It is slightly anticonservative in the presence of loss to follow-up.

The DFS estimate and its confidence interval will be compared to similar statistics observed for patients treated with standard care fractionation schedules such as those presented in [Zelefsky et al. High dose rate radiotherapy delivered by intensity modulated conformal radiotherapy improves the outcome of localized prostate cancer, J. Urol. 166: 876, 2001]. In addition, efficacy in these data will be modeled with the linear-quadratic formula [Chappell, R., Nondahl, D., and Fowler, J.F. Modeling dose and local control in radiotherapy. Journal of the American Statistical Association. Vol. 90 (1995), pp. 829-838] to examine the hypothesis, which underlies the logic of fractionation, that prostate cancers have an alpha/beta ratio which makes them better able to repair radiation injury than surrounding late responding tissues.

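### The DFS definition does not say how the start of salvage therapy is scored, so a man with a nadir below 1.0 ng/mL who starts it after one or two PSA rises counts as recurrence-free

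*Combined protocol and SAP*

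**What the plan says.** Section 8.2 states: "A primary endpoint is Disease-Free Survival (DFS), as defined in Section 6.2". Section 6.2 sets four conditions for being free of recurrence.

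- The first has two limbs. The opening limb reads "Patients will be considered to be without biochemical recurrence if either the PSA is still declining". The second limb, which suffices on its own, reads "or the PSA nadir has been reached and is below 1.0 ng/mL".
- Neither palpation nor imaging shows disease.
- The third condition reads "PSA is not rising (defined as 3 successive increases in measured PSA levels each at least two months apart").
- Metastasis is absent.

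A man who does not meet these conditions is scored as a recurrence. Section 6.3 adds: "Any patient with rising PSA on 3 successive serum measurements will be considered to have recurrent or progressive disease". It dates that failure midway between the nadir and the first of the three rises.

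The plan mentions hormone treatment only in the eligibility list of Section 3.0: "Gonadotropin-releasing hormone agonist (GnRH-a) use permitted (maximum of 6 months duration"), with anti-androgen allowed alongside. That allowance is not linked to endpoint scoring. Section 7.3, footnote a, sets the visits at which PSA is measured: "Subsequent follow-up will be every 3 months x 1 year post-treatment, every 4 months during years 2 - 3". Visits are six-monthly in the fourth and fifth years and yearly after that, and more frequent visits are allowed. Section 9.0 commits to collecting the items in the Section 7.0 table, which has no row for later anticancer therapy.

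**The concern.** Nothing in the plan ties the scoring of DFS to whether new anticancer therapy has begun. If such therapy starts after one or two rises and lowers PSA, the run of three successive rises is broken and Section 6.3 is not triggered. The man can then satisfy every condition of Section 6.2 for as long as the suppression lasts.

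Three uses of the endpoint are affected: the DFS estimate and its confidence interval (8.2), the linear-quadratic modelling of efficacy (8.2), and the failure outcome in the biomarker Cox model (8.3). The interval in 8.2 reflects sampling error, and the only data problem that section mentions is loss to follow-up. A systematic misclassification of failures lies outside the interval.

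This is a different problem from PSA recovery after the permitted GnRH agonist course. That recovery could create false failures; this gap hides or delays true ones.

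**Working it through.** **1. Applying the rule to a man treated after one or two rises, with no clinical disease**

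- Post-radiation nadir below 1.0 ng/mL: he meets the second limb of the PSA condition, has not had three rises and has no metastasis. He is recurrence-free under 6.2, and 6.3 is not met.
- Post-radiation nadir of 1.0 ng/mL or higher: the result depends on how the nadir is read. If the pre-salvage value is binding and PSA no longer counts as still declining after a rise, he fails both limbs and is scored as a recurrence. If a drug-induced low below 1.0 counts as the nadir, he passes. The text does not settle this.
- Failure date: the midpoint rule in 6.3 needs the first of three rises. A man with fewer than three has no date under that rule, and no dated treatment field exists from which to assign one later.

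**2. Length of the window**

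Treatment after one or two rises falls between the first and third rise, which is two visit intervals.

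- Years 2–3: 2 × 4 = 8 months.
- Years 4–5: 2 × 6 = 12 months.
- With added visits at the two-month minimum spacing in 6.2: 2 × 2 = 4 months.

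**3. The plan's precision figure**

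The half-width is 1.96 × √(p(1 − p)/150).

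- At p = 0.50: 0.0800, or 8.0 points. This reproduces the 8% in Section 8.2.
- At p = 0.85: 0.0571, or 5.7 points.

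**4. Size of the overstatement**

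Inputs: n = 150 (8.2); five-year failure rate F = 15% (8.3); 250 patients in the biomarker model (8.3). The share f of failures hidden by salvage before a third rise is not in the documents. The range 10% to 33% is an assumption, and the formula supposes that no hidden failure is picked up later.

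Observed DFS = 1 − F(1 − f), so the overstatement is F × f. Expected failures are 150 × 0.15 = 22.5; expected biomarker events are 250 × 0.15 = 37.5.

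| f (assumed) | Men hidden, 22.5 × f | DFS overstated, 15 × f (points) | Biomarker events lost, 37.5 × f |
|---|---|---|---|
| 10% | 2.25 | 1.5 | 3.75 |
| 20% | 4.5 | 3.0 | 7.5 |
| 33% | 7.4 | 5.0 | 12.4 |

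The overstatement equals the 5.7-point half-width when f = 5.71/15, about 38%.

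**The case against.** The strongest reply is that 6.2 is less permissive than it looks, and that the size of the effect is unknown.

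- A reader might infer that any man started on hormones is scored disease-free because his PSA is falling again. The wording does not support that. After a rise, PSA is no longer still declining in the ordinary sense, so the route is mainly the limb for a nadir below 1.0. A man with a higher nadir may already be a failure, because 6.2 scores as a recurrence anyone who does not meet its criteria. This limits the point but does not remove it.
- A reader might measure the window from the nadir visit, which gives three intervals: 12 or 18 months. The relevant span starts at the first rise and is two intervals, or less if visits are added.
- Section 5.8 continues disease follow-up until progression. Later rises, palpable disease or metastasis would still count, so some failures would be delayed and not lost. The tabulated figures are therefore upper bounds for each assumed share.
- A reader might infer a bias in favour of hypofractionation against the published series named in 8.2. The documents do not say how those series score salvage. If they use a similar rule, the effect falls on both sides. Only an upward bias in the absolute DFS estimate is supported.
- Every overstatement in the assumed range is smaller than the 5.7-point half-width. That is correct, but sampling error shrinks with more patients and this error does not.

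No part of the plan supplies the missing rule.

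**Conclusion.** The omission is certain. For men with a nadir below 1.0 ng/mL and no clinical disease, the rule as written returns the wrong status, so this is more than missing detail. For men with a nadir of 1.0 or higher, the result depends on an undefined reading of the nadir.

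The direction for absolute DFS is upward, and events in the biomarker model are removed or delayed. The size cannot be derived from the documents. The limits of 1.5, 3.0 and 5.0 points rest on the plan's 15% failure rate, the assumed shares of 10%, 20% and 33%, and no later recapture. No conclusion is drawn about bias relative to the published comparison series.

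The sponsor should correct this because DFS is a primary endpoint and, without a dated field, the scoring may not be recoverable afterwards.

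**What to change.** - **Scoring.** Add to 6.2 and 6.3 that starting non-protocol anticancer therapy for suspected or proven recurrence before three rises is a DFS failure, dated at the start of that therapy. Define such therapy as salvage local therapy, or androgen deprivation other than the GnRH agonist course planned at entry under 3.0.
- **Dating.** State that this date differs from the midpoint rule in 6.3, so that the two kinds of failure are knowingly dated differently.
- **Data.** Add the type, reason and start date of such therapy to the 7.3 follow-up items. Because 3.0 gives a maximum duration but no timing, record the planned hormone course at entry so that it can be told apart from salvage.
- **Sensitivity analysis.** Report DFS with censoring at the start of such therapy, noting that this censoring may be informative.

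The cost is a few sentences and a small number of dated fields. The planned sample size is unchanged. The downside is that some men treated before a confirmed third rise will count as failures, including men treated for PSA recovery after the permitted hormone course. Reported DFS becomes slightly less favourable. The change concerns scoring only and takes no position on whether or when salvage therapy is given.

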6.3 Progressive Disease

Any patient with rising PSA on 3 successive serum measurements will be considered to have recurrent or progressive disease. The date of failure will be taken as midway between the nadir PSA date and the date of the first of the three rising PSAs.

7.0 STUDY PARAMETERS

7.1 All pre-study laboratory tests must be done within 6 weeks of registration.

7.2 Patients will be evaluated weekly during radiotherapy by one of the clinical study investigators to assess acute toxicities and functional status

7.3. The follow-up schedule and evaluations are outlined below:

	Pre-study	Weekly during RT	4 weeks post-RT	3 months post-RT	Subsequent follow-up ^a
H & P	X		X	X	X
Weight	X	X	X	X	X
Performance status	X	X	X	X	X
PSA	X		X	X	X
CBC/platelets	X				
Toxicity notation	X	X	X	X	X
QOL assessment	X				X ^b
IPSS score	X		X	X	X

^a Subsequent follow-up will be every 3 months x 1 year post-treatment, every 4 months during years 2 - 3, every 6 months years 4 – 5 and then annually. Follow-up frequency can be increased if thought medically necessary by the treating physician

^b QOL assessment will be completed pre-treatment and at 12, and 24 and 36 months post-treatment.

* For patients for whom travel to the treating institution creates a hardship, scheduled follow-ups, with the exception of the 4 week and all annual follow-ups, can be conducted via telephone interview with PSA and any other indicated testing being carried out at a facility near to the patient.

8.0 STATISTICAL CONSIDERATIONS

8.1 Treatment and Toxicities

This phase I/II trial will be conducted with three potential fraction size levels, with a potential of 50 patients per level (plus an additional 100 patients at MTS if permitted by the escalation rules) and an accrual rate of approximately 50 patients per year anticipated. This may estimate the maximum tolerated dose-per-fraction (MTD), defined as that fractionation schema that yields at most a 40% rate of late grade 2 rectal toxicity at 2 years. A modified LENT grading system for rectal toxicity will be used (28). That outcome is chosen for its clinical relevance; however, the extended follow-up makes the standard sequential designs impractically long at 3 years (one year accrual plus two years follow-up for each of three cohorts). We therefore use the simply modified class of prorated designs (R. Chappell and K. Cheung, Simple designs for phase I clinical trials of long-term toxicities, abstract presented at the 1998 meeting of the Society for Clinical Trials). Proration implies, for example, that two patients observed for one year each, constituting two patient-years of follow-up, are equivalent in information to one patient followed for two years. This implicitly uses the result of Teshima (29) that the cumulative incidence of late grade 2 rectal complications reaches 50% of the final value within twelve months of treatment and that the cumulative incidence of complications is approximately linear with time.

The prorated design will require the following conditions for escalation: at least twenty patient-years of observation; and a minimum of 5 patients followed for one year; and at most a 40% toxicity rate per two years (i.e., at most 2 toxicities per 10 patient-years) observed. Proration allows a great reduction in the overall time of the trial - with fifty patients accrued at a uniform rate over each year, the first two conditions will be satisfied after 15 months. Thus the entire study will take at most 45 months. The requirement of 5 patients being followed for one year is made for safety's sake. The situation may arise that the maximum 50 patients have been accrued at a particular dose-per-fraction step, but there is insufficient follow-up to allow escalation to the next dose-per-fraction step. Under these circumstances, additional patients may be accrued at the previous (next lower) dose-per-fraction level until follow-up conditions for the next escalation are met.

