5.2 Dose-per fraction escalation

Escalation to the next higher dose-per-fraction level (or the accrual of an additional 100 patients to the MTS) will only be allowed when there is at least 20 patient years of follow-up and at least 5 patients have been followed for at least 12 months. A rate of 20% grade 2 or higher late rectal toxicity per patient follow-up year will be considered dose limiting. Late toxicities will be scored > 90 days from completion of therapy. The statistical rationale and methodology for this dose-per-fraction escalation strategy is described in section 8.0. Of note, statistical fluctuations in measured toxicity rates could occasionally lead to an initial over- or underestimation of these rates. Therefore, cumulative toxicity rates will be updated every 6 months throughout the life of the protocol and will be utilized according to the rules stated above.

The expected accrual timetable, the proposed dose-per-fraction and total fraction levels, and patient accrual goals for this phase I/II trial are shown in Table 1 below.

Table 1: Fraction size dose escalation protocol

Level	Approx. Interval (mo)	Dose per Fx (Gy)	# Fxs	# pts	Treatments per week	Total dose (Gy)	Equiv. dose (Gy)
I	1-15	2.94	22	50*	3 ← 4 → 5	64.68	82.6
II	16 - 30	3.63	16	50	3 ← 4 → 5	58.08	85.1
III	31 - 45	4.3	12	50	3 ← 4 → 5	51.6	85.5

* See section 5.1 for exceptions. Patients are initially treated 3 or 4 times per week, with this treatment frequency subsequently increasing, decreasing or remaining the same based upon the number of acute toxicities observed, as described in Section 5.3.

All of the three above levels are predicted to be approximately isoeffective for late effects at BED_3 equals approximately 128 Gy₃. In other words, each of these dose-per-fraction levels would be predicted to produce about the same level of late toxicity, all other factors such as high dose rectal wall volume remaining constant. Furthermore, the above schemas are all predicted to produce the same late toxicity as the fractionation regimen successfully piloted by Kupelian and Mohan(23) of 2.5 Gy times 28 fractions.

An additional **100** patients may be accrued to the MTS if toxicities observed in the first patients at the level are within the limits specified in the standard escalation rules.

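### The escalation rate matches the 40%-at-2-years limit only under patient-time conventions that the plan never states; uncapped, it falls well below the true rate at later six-monthly updates

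*Combined protocol and SAP*

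**What the plan says.** Section 8.1 defines the maximum tolerated schedule by late grade 2 rectal toxicity of at most 40% at 2 years, and 5.6.2 gives the same limit for grade 2 or higher. To avoid waiting two years per cohort, 8.1 uses a prorated rule that requires "at most a 40% toxicity rate per two years (i.e., at most 2 toxicities per 10 patient-years) observed". Its justification is that "two patients observed for one year each, constituting two patient-years of follow-up, are equivalent in information to one patient followed for two years". This rests on a cited study in which half of the eventual complications had appeared by one year, and on the premise that "the cumulative incidence of complications is approximately linear with time".

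Section 5.2 states the limit per year: "A rate of 20% grade 2 or higher late rectal toxicity per patient follow-up year will be considered dose limiting". It sets the minimum information as "at least 20 patient years of follow-up and at least 5 patients have been followed for at least 12 months" and restricts the events that count: "Late toxicities will be scored > 90 days from completion of therapy". It then has cumulative rates recalculated every six months for as long as the protocol runs, and used under the same rules.

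On timing, 8.1 says that "with fifty patients accrued at a uniform rate over each year, the first two conditions will be satisfied after 15 months".

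No section says when patient-time starts, whether it is limited to two years per patient, or whether it ends at the first event. The nearest hints are the reference to twelve months of treatment in 8.1 and the post-treatment visit schedule in 7.3.

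**The concern.** The ratio of late rectal events to patient-years governs escalation, continued accrual at a level (5.1) and the extra 100 patients at the selected schedule. A rate per year stands in for a two-year cumulative risk only over the window in which that risk builds up. Section 8.1 puts half of the final incidence within twelve months and treats the rise as linear, which implies completion at about 24 months. After that, a patient adds time but almost no events. A cumulative rate with no cap must then drift down, whatever the true two-year risk. Handling of events matters as well: stopping time at the event shortens the denominator and changes what 0.20 per year means. An undefined start leaves the permitted number of events open at the first look. Two analysts following the text could therefore reach different decisions from the same data, and later updates could make a level above the limit look acceptable.

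**Working it through.** **Inputs.** From 8.1: 50 patients entered evenly over 12 months, first look at month 15, at most 0.20 events per patient-year, 40% at 2 years. From 5.2: 22 fractions at Level I and late scoring after 90 days. From 1.5: an initial 4 fractions per week, so radiotherapy lasts 22/4 = 5.5 weeks = 1.265 months; 90 days = 2.957 months. Assumptions: treatment starts at registration, no treatment breaks, no loss to follow-up, incidence complete 24 months after radiotherapy. Months count from the opening of the level.

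**1. The plan's conversion.** 0.40 / 2 years = 0.20 per patient-year, or 2 per 10. It reproduces. If incidence is linear from the end of radiotherapy and time starts there, the month-15 data hold 32.2 patient-years and 32.2/2 = 16.1 expected shares of the two-year incidence. A true 40% then reads 0.40 × 16.1 / 32.2 = 20.0%.

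**2. The plan's timetable.** With evenly spaced entries the fifth patient enters at about month 1.08. The one-year condition is then met at:
- registration start: 1.08 + 12 = month 13.1
- end-of-radiotherapy start: 1.08 + 12 + 1.265 = month 14.3
- day-90 start: 1.08 + 12 + 1.265 + 2.957 = month 17.3

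Twenty patient-years are reached at months 10.7, 12.0 and 15.0 respectively, so the one-year condition decides. The first two starts fit the stated 15 months. A day-90 start used for both conditions does not.

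**3. Events allowed at the first look.** Once every patient has started to contribute, patient-years = 50 × (T − 6 − lag)/12, where lag is the delay from registration to the start of patient-time.

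| Start | Month 15 | Allowed | Month 17.3 | Allowed |
|---|---|---|---|---|
| Registration | 50 × 9/12 = 37.5 | 7.5 → 7 | 50 × 11.3/12 = 47.1 | 9.4 → 9 |
| End of radiotherapy | 50 × 7.735/12 = 32.2 | 6.4 → 6 | 50 × 10.035/12 = 41.8 | 8.4 → 8 |
| Day 90 | minimums not met | – | 50 × 7.078/12 = 29.5 | 5.9 → 5 |

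**4. Later updates, no cap, time continuing after the event, end-of-radiotherapy start, closed level of 50, true rate 40%.** Patient-years = 50 × (T − 7.265)/12. The last patient passes 24 months at 12 + 1.265 + 24 = month 37.3, so at months 39 and 45 the expected events are 0.40 × 50 = 20 whatever the shape of the curve.
- Month 33: 107.2 patient-years; with half the incidence by month 12 the expected shares sum to 48.4, so 0.40 × 48.4 / 107.2 = 18.1%
- Month 39: 20 / 132.2 = 15.1%
- Month 45: 20 / 157.2 = 12.7%
- Months 39 and 45 with each patient capped at 24 months: 20 / (50 × 2) = 20.0%

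The true rate that would read 20% is 0.20 × 132.2 / 50 = 52.9% at month 39 and 0.20 × 157.2 / 50 = 62.9% at month 45.

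New accrual softens this but does not remove it. If the extra 100 patients enter at 50 per year over months 15 to 39 (assumed), the level has 222.0 patient-years at month 39 and a true 40% reads 16.5%, with half the incidence by month 12.

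**5. Time stopping at the event.** A constant 0.20 per year gives 1 − exp(−0.20 × 2) = 33.0% at two years; 40% would correspond to −ln(0.6)/2 = 0.255 per year. With linear incidence over a full two years, 40% corresponds to 0.40/(2 − 0.40) = 0.25. Without a cap, the closed level with a true 40% reads 22.7%, 19.9% and 17.3% at months 33, 39 and 45.

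**6. Dependence on the curve at month 15.** On the end-of-radiotherapy start a true 40% reads 16.5% (nothing to day 90, half by month 12), 14.3% (linear from day 90), 19.7% (60% by month 12) or 20.0% (linear from the end of radiotherapy).

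**The case against.** The strongest defence is that the conversion is right on its own terms. Under the proration in 8.1, 0.40/2 is exactly 0.20, and step 1 confirms it. A reader might infer that 2 per 10 patient-years simply fails to represent 40% at 2 years. The documents do not support that. It fails only when unscorable time enters the denominator, time stops at the event, or follow-up runs past two years.

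A reader might also count patient-years from day 90 (20.2 at month 15), allow only 4 events, and conclude that the choice of clock reverses the month-15 decision in about one trial in three at a true 40%. That combines a day-90 start for patient-years with a one-year condition measured from the end of radiotherapy. On a single day-90 start no patient has a year of follow-up at month 15. The spread at the first look also comes from the start alone, because nobody is near two years by then.

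Nor do the documents establish that the first look is biased in a given direction. Step 6 runs from clearly low to exact, and by month 21 the first three curves read 19.6%, 17.9% and 22.1%.

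It can further be said that 5.2 already warns of early over- or underestimation, that 5.6.2 states the two-year limit directly, and that a late reading on a closed level may drive no accrual decision. The warning concerns chance fluctuation, whereas dilution is systematic and grows with follow-up. Section 5.2 sends the updates back to the per-year rule and does not say when the direct limit takes over. The last argument stands in part, but 4.0 and 8.1 allow accrual to return to the next lower level, and the 100-patient expansion keeps a level open while its older patients pass two years.

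**Conclusion.** The point holds in this form. The rate rule equals the 40% limit only with incidence linear from the start of the clock, at most two years per patient, and time continuing after the event. The plan assumes approximate linearity but states no start, cap or event rule, and it applies the rate repeatedly to cumulative data.

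The main consequence is at later updates. With no cap and no stop, a closed level at a true 40% reads about 18.1%, 15.1% and 12.7% per year at months 33, 39 and 45, and a true rate near 53% or 63% would still read 20% at the last two. This rests on incidence being complete by 24 months after radiotherapy, complete follow-up and an end-of-radiotherapy start. The month-39 and month-45 figures need no further assumption about the curve; month 33 uses half the incidence by month 12.

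At the first look the consequence is smaller: 7 against 6 events at month 15 for Level I at 4 fractions per week, or 5 against 8 or 9 at about month 17.3 if a day-90 start is used throughout. The size and direction of any month-15 bias remain undetermined. This should be fixed. Confidence is medium, because the team may already apply conventions that the document does not record.

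**What to change.** Reconcile 5.2, 5.6.2 and 8.1.

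1. State one start for patient-time, used for both the patient-years and the one-year condition, and say whether time stops at the event.
2. Cap each patient's contribution at the two-year window on which the 40% limit is defined, and give the conversion between rate and limit under that same convention.
3. Once patients reach 24 months, base the six-monthly updates on a time-to-event estimate of two-year incidence, and state when it replaces the prorated rate.

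The choice of start and any restated threshold belong to the sponsor; no new dose-limiting value is proposed here. The cost is wording in three sections and a little more analysis work, with no extra patients. The downside is that late readings will be less favourable than the uncapped rate.
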